SH+ programme has two components: a pre-recorded course and a self-help book. Pre-recorded audio material (locally adapted) is delivered across five 2-hour sessions and in groups of 10 to 40 people. In order to be in accordance with the cultural norms and the preferences of target community, single gender groups will take place. The audio material imparts key information about stress management and guides participants through individual exercises and small group discussions. A written facilitator guide helps briefly trained non-specialist facilitators to conduct the course using these audio materials. To augment the course materials, an illustrated self-help book reviews all essential content and concepts. The book contains more than 400 illustrations and conveys key points with minimal text. It was written to be useful both as a standalone product and as a key resource for those participating in the course (8). The format of SH+ is innovative in that it seeks to ensure that key intervention components are delivered as intended through the use of pre-recorded audio, without the burden of extensive training and supervision.

SH+ programme is based on acceptance and commitment therapy (ACT), a form of cognitive-behavioral therapy, with distinct features (54). ACT is based on the concept that ongoing attempts to suppress unwanted thoughts and feelings can paradoxically make these problems worse. Instead, it emphasizes learning new ways to accommodate difficult thoughts and feelings – primarily through mindfulness approaches – without letting them dominate, while guiding people to take proactive steps towards living in a way that is consistent with their values. ACT has been shown to be useful for a range of mental health issues (55) and has been used successfully in a guided self-help format (56). More specifically, SH+ includes ACT techniques that aim to reduce stress, live in accordance with ones values and to increase social support.

Delivery of SH+

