Control arm participants will receive routine social support and/or care according to ordinary practice and following local regulations. Additionally, they will receive baseline and followup assessments according to the study schedule, and information about freely available mental health services, social services and community networks providing support to people under temporary protection of Turkey and refugees, and NGOs' contact details. A member of the research team will preliminary inform local NGOs and community networks about this trial. The follow-up assessments will consist of interviews with members of the research team, and imply the creation of a supportive environment and a regular clinical assessment and the possibility of interacting with local NGOs' for receiving information on any issues related to social integration and support. However, as the control arm will include only participants without a psychiatric diagnosis, they will not be connected with mental health services, in order to avoid medicalization of their condition of psychological distress. In case some participants in the control group develop a mental health condition during the study, they will be connected with mental health services (as reported above).. In comparison, refugees that are excluded because of a diagnosis of a mental disorder will be actively connected to professional treatment and contacts with local mental health care services which will be facilitated by members of the research team (as reported above).

In this trial, in agreement with the regulations in Turkey, study participants will receive the same interventions provided to the local general population with the same psychological condition. People from the general population who are experiencing emotional distress but do not meet criteria for a diagnosis of mental disorder are usually provided with information on how to access health care services, including primary health care services and emergency services. Additionally, they are also referred to social support services, including social care facilities, charities, NGOs and other community resources. The NGOs that will take part in this study by referring potential participants from their beneficiries and providing logistic support will provide both informal and psychosocial support to the participants in the ETAU group. All these interventions will be offered to study participants at baseline and at each follow-up visit.

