By contrast, for individuals with a mental disorder guidelines generally state they should receive health services. The above approach is consistent with these guidelines as it provides a) referral to services where a mental disorder is indicated at baseline (e.g. excluded from trial), b) information on available health services and support services (e.g. NGOs) for individuals accepted into the trial (distress but no mental disorder), c) ongoing assessment and referral to services for individuals in the trial who later develop a mental disorder.

SAFETY CONSIDERATIONS AND FOLLOW UP

Adverse events reporting

Serious adverse events and other adverse events reported spontaneously by the participants or observed by research or intervention staff will be recorded in a form specifically developed for adverse events reporting (see example form in Appendix 9). Data on the relationship with the study intervention, the action taken regarding intervention and the outcome of the adverse event will be collected.

An event is considered a potential adverse reaction if it is an undesirable experience occurring to a participant during the study, whether or not considered related to the research procedure. This definition includes all aspects of mental health and psychological functioning, but also any undesirable experiences. The chair or a nominated person from the Ethics Advisory Board (EAB - see Appendix 2) will review spontaneously reported serious adverse reactions (i.e., suicide attempts) within 48h, deciding if it is likely related or unrelated to the intervention. General adverse reactions will be reviewed by the EAB in regular bi-monthly meetings. In both instances, the EAB will determine if any appropriate action in respect of ongoing trial conduct is necessary and specify what action this would be (i.e. referral to specialized care). The site Principal Investigator will be responsible for ensuring that required actions are implemented. The site Principal Investigator will also inform trial participants and those bodies providing ethical oversight if anything occurs on the basis of which it appears that the disadvantages of participation may be significantly greater than was foreseen. SOPs will be prepared and followed for adverse events reporting.

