- Benefits in terms of psychological symptoms and functioning, quality of relationships, and solutions of specific problems both related and unrelated to their traumatic experiences, breaking of unhealthy patterns, and a significant reduction in feelings of distress.
- Contributing to a research that may limit the incidence of newly diagnosed psychiatric disorders in refugees resettled in Turkey.

Potential risks

- There are no guarantees of what participants will experience, and of the duration of changes. For example, it could be that benefits won't last for long periods;
- Based on data from randomized controlled trials already testing the SH+ we are not expecting the intervention worsening mental health condition of participants. However, it could be that participants will experience a transient increase of their mental health problems. In order to mitigate these risks, follow-up assessments and networking with NGOs have been planned to closely monitor the psychological status of participants. In addition facilitators will be trained in basic helping skills and identification of serious adverse events (e.g. imminent risk of suicide) which will further aid identification of any adverse reactions to SH+. Facilitators will be regularly supervised by mental health professionals to further address this risk;
- Participants will not be able to choose in which study arm they will be allocated;
- Participants might experience uncomfortable feelings like sadness, guilt, anger, frustration, and loneliness. Approaching feelings that participants have tried to avoid for a short or long period of time may be painful;
- The participant burden related to the involvement in this study may compete with ongoing responsibilities faced by newly re-settled people (i.e., housing, language issues, new medical system, etc.). This issue has been considered when planning study timeline and assessments. The study is pragmatic and participation implies only 4 assessments of 1 hour each. However, it will be taken into careful consideration throughout the course of the study;
- Participants might feel uncomfortable in a group setting.

INFORMED CONSENT FORMS

Three informed consent forms specific to Turkey have been prepared and attached:

- 1) one for screening (for the pilot or trial phase) (Appendix 3)
- 2) one for participation in the trial phase RCT (Appendix 4)
- 3) one for participation in the pilot (Appendix 5, with differences from Appendix 4 highlighted in green).

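### Adverse events are captured passively and SH+ has five extra staff contacts, so counts of recorded events carry a detection bias between arms that the masked scales only partly offset.

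*Protocol*

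**What the plan says.** The section *Adverse events reporting* sets the capture rule: "Serious adverse events and other adverse events reported spontaneously by the participants or observed by research or intervention staff will be recorded". Its definition of an adverse reaction covers mental health and functioning and extends to any other undesirable experience, whether or not related to the research. The form also collects relatedness, action taken and outcome. An example is placed in Appendix 9, and procedural detail is left to SOPs; neither is shown.

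The same section has the chair of the Ethics Advisory Board (EAB), or a nominee, review serious reactions within 48 hours, and the board review other reactions every two months. In both cases "the EAB will determine if any appropriate action in respect of ongoing trial conduct is necessary".

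Contact with staff differs by arm. The SH+ course "is delivered across five 2-hour sessions and in groups of 10 to 40 people". Under *Potential risks*, "facilitators will be trained in basic helping skills and identification of serious adverse events (e.g. imminent risk of suicide". Of control participants, *Enhanced Treatment as Usual* says that "they will receive baseline and followup assessments according to the study schedule". They also receive support from NGOs, whose staff are not named as recorders of adverse events. For everyone, "participation implies only 4 assessments of 1 hour each": one at baseline and three after randomisation, the latter by masked assessors. The assessment lists and Table 1 give the M.I.N.I. and the symptom scales at those three visits, and no adverse-event question.

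**The concern.** There are two routes for recording an event, the participant volunteering it and staff noticing it. Both depend on contact, and planned contact is unequal by design. The extra SH+ contact falls in the weeks of exposure, when the effect the protocol itself foresees ("it could be that participants will experience a transient increase of their mental health problems") would most plausibly appear.

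If the plan is followed exactly, an excess of recorded events in SH+ could be real harm or simply more opportunity to record. Equal counts could likewise conceal a true reduction. No later analysis can recover events that were never elicited equally, or sort events by route if the route was not recorded. This is therefore a matter of data collection and cannot be left to the analysis plan.

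**Working it through.** The protocol gives no figure for adverse events, so none can be reproduced. Its sample-size figure (25% against 15%, 250 per arm, 80% power) does reproduce but has no bearing here. Only the 300 randomised per arm is used below.

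**Planned contacts after randomisation**

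- SH+: 5 sessions + 3 assessments = 8.
- ETAU: 3 assessments. The frequency of NGO contact is not stated and NGO staff are not named as recorders, so it counts as zero.
- Ratio: 8/3 = 2.67.
- Up to and including the post-intervention visit: 5 + 1 = 6 against 1.

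These counts assume full attendance. After the sessions end, scheduled contact is the same in both arms.

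**Illustration of what unequal contact can do**

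Assumptions, none of them in the documents: the true risk is equal in both arms; each contact has the same probability q of bringing an event to record; contacts are independent; and every contact can reveal the event. The share of events recorded is then 1 − (1 − q)^k, with k = 3 for ETAU and k = 8 for SH+. For q = 0.1 this gives 1 − 0.9³ = 0.271 and 1 − 0.9⁸ = 0.570, a ratio of 2.10.

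The last column is the chance of a nominally significant difference at two-sided 0.05 with n = 300 per arm. It uses Φ{[|p₁ − p₀| − 1.96√(2p̄(1 − p̄)/n)] / √([p₀(1 − p₀) + p₁(1 − p₁)]/n)}, where p₀ and p₁ are the recorded risks and p̄ is their mean. For q = 0.1 and a true risk of 10%, p₀ = 0.0271 and p₁ = 0.0570.

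| q | Recorded, ETAU | Recorded, SH+ | Ratio at equal true risk | Chance of a nominal difference, true risk 5% / 10% / 20% |
|---|---|---|---|---|
| 0.1 | 0.271 | 0.570 | 2.10 | 0.246 / 0.445 / 0.752 |
| 0.2 | 0.488 | 0.832 | 1.71 | 0.217 / 0.396 / 0.703 |
| 0.3 | 0.657 | 0.942 | 1.43 | 0.143 / 0.251 / 0.479 |
| 0.5 | 0.875 | 0.996 | 1.14 | 0.054 / 0.073 / 0.115 |

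The ratio approaches 2.67 only as q approaches zero, and it shrinks as detection improves. The table shows direction and sensitivity; it does not estimate the bias in this trial.

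**What the equally administered measures cover**

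- The M.I.N.I. outcome is a current diagnosis. The PHQ-9 looks back two weeks, the adapted PCL-5 one week and the WHODAS 30 days.
- The post-intervention visit falls 0–1 week after a course of about five weeks. The next visit is six months after randomisation: about 26 − 6 = 20 weeks later. The one after that follows a further six months on.
- Worsening that is still present at a visit is measured equally. Worsening that resolves between visits, and undesirable experiences outside mental health, can be missed by these scales although the protocol counts both.

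**After the change**

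With the same question at the three common visits, planned elicitation is 3 against 3. Under the same assumptions the ratio is 1.0.

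**The case against.** The other side has a good deal of substance.

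- **The main harms are measured well.** A reader might infer that harms cannot be compared between arms at all. The documents do not support that. New diagnoses, distress, depression, PTSD symptoms and functioning are assessed on one schedule, in both arms, by masked assessors, first within about a week of the course ending. The service-use inventory also gives both arms some record of health care at 6 and 12 months. This stands, and it confines the point to recorded adverse events.
- **The contact ratio is not an event ratio.** A reader might infer up to 2.7 times as many events in SH+. That would require a group session run from recorded audio to prompt as much reporting as a one-hour interview, and would ignore that an event missed at a session can be volunteered at the next visit. This stands.
- **The EAB is not given counts by arm.** A reader might infer that the board will be misled by an imbalance. The protocol describes review of individual reports, with relatedness judged event by event, and states no between-arm test of adverse events. This stands. It lowers the stakes, but any tabulation by arm would still inherit the bias.
- **Control-arm events are not simply lost.** Volunteered reports are not confined to visits, and after the course both arms have the same gaps. Facilitators are trained to identify serious events, not every kind. This also stands.
- **The SOPs or the Appendix 9 form may add a question.** Possible, but the rule the protocol states is that events are recorded when "reported spontaneously by the participants or observed by research or intervention staff will be recorded", and one of those staff groups meets only one arm.
- **The likely error overstates SH+ harm and leaves the primary outcome untouched.** True, though an excess readily explained away as a contact effect also makes a real harm harder to recognise.

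**Conclusion.** The point holds in a limited form. The stated capture rule is passive, and planned contact is 8 against 3 (6 against 1 through the post-intervention visit). Counts of recorded adverse events are therefore likely to lean towards SH+ and cannot be compared between arms free of detection bias. The direction rests on the assumption that more contact brings more events to record. The size cannot be derived from the documents: the ratios of 1.14 to 2.10 depend wholly on an assumed detection probability and equal true risk. Comparisons of diagnosis and symptom scores at the masked visits are unaffected. What is left without an even-handed measure is transient events between visits and undesirable experiences outside mental health. This is an inexpensive improvement to data collection, and it does not threaten the trial's primary result.

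**What to change.** At the post-intervention, 6-month and 12-month visits, ask every participant in both arms one standard open question about undesirable events since the previous assessment visit. Anchoring it to the assessment, and not to the last session, gives both arms the same recall period. Place it after all outcome measures, so that an answer cannot reveal the allocation before that visit's ratings are complete.

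Add a source field to the event form: elicited at a visit, volunteered, or seen by a facilitator. Base any between-arm summary on visit-elicited events, and keep every other report for individual EAB review as now. If the SOPs or the Appendix 9 form already contain such a question, state it in the protocol and add it to Table 1.

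The cost is one question at visits that already take place, one extra field, and more event forms to process. A small risk of unmasking remains, since an assessor who hears about the sessions at one visit may rate the same participant at a later one.

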The statistical analysis will be masked. The trial statistician will be blinded to the treatment groups until the analysis has been completed. Moreover, the trial statistician will not be involved in determining participants' eligibility, in administering the intervention, in measuring the outcomes, or in entering data (data will be entered with a double-entry procedure). All analyses will be performed using Stata/SE, Release 14.2.

Two data locks will occur during the study. The first one will happen 6 months after the end of the 12-month enrolment period (month 18 from study beginning), when the information on the primary outcome and on the short-term secondary outcomes will be available for all study participants. The second one will happen at the end of the study (month 24 from study beginning), when information on the long-term secondary outcomes will be available for all participants.

All primary and secondary analyses will be performed on an intention-to-treat (ITT) basis. The ITT population will consist of all participants randomly assigned to the competitive intervention strategies. In order to check the robustness of results, the primary outcome will be additionally analysed using a per protocol (PP) approach, that will include only participants who fulfil the protocol in terms of eligibility, interventions, outcomes assessment at follow-

ups. The analysis of the PP population will be used for confirmatory purposes only. If less than 5% of participants does not receive the allocated intervention according to the study protocol, the PP analysis will not be performed.

All analyses reaching statistical significance will be replicated for each recruiting centre and for each population group separately. In addition, all analyses reaching statistical significance will be stratified by methods of assessment (face to face versus telephone or secure online audio/video communication).

Analysis of the primary outcome

The proportion of participants with a psychiatric diagnosis at 6-months follow-up will be compared between the two groups through the chi-square test (primary analysis). A multivariate analysis (secondary analysis) will be performed through a Poisson regression model, with a robust error variance (57), to estimate relative risks directly and to explore the potential confounding effect of prognostic factors, and the interactions with treatment.

Analysis of the secondary outcomes

Secondary outcomes are:

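### The per-protocol check compares self-selected SH+ attenders with nearly all assessed controls, so it can differ from ITT through selection alone

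*Protocol*

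**What the plan says.** All the relevant rules are in the Protocol, Statistical Analysis, General approach. The basis is ITT: "All primary and secondary analyses will be performed on an intention-to-treat (ITT) basis". The PP analysis comes on top of that: "In order to check the robustness of results, the primary outcome will be additionally analysed using a per protocol (PP) approach". The PP set will "include only participants who fulfil the protocol in terms of eligibility, interventions, outcomes assessment at follow" (the last word continues as follow-ups). Three grounds for exclusion are named, and no arm is named. On its use the protocol says "The analysis of the PP population will be used for confirmatory purposes only", and on when it is run, "If less than 5% of participants does not receive the allocated intervention according to the study protocol, the PP analysis will not be performed".

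The primary outcome "will be compared between the two groups through the chi-square test (primary analysis"), an unadjusted test. No adjustment specific to the PP set is stated.

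The two interventions differ in what a participant can miss. The SH+ audio material "is delivered across five 2-hour sessions and in groups of 10 to 40 people" (The Self Help Plus (SH+) programme). Under Enhanced Treatment as Usual (ETAU), controls receive routine support, information about services, and assessments. There are no sessions to complete.

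**The concern.** A robustness check should show whether the ITT result survives a change in how deviations are handled. This one changes who is compared. Non-attendance can occur on a meaningful scale only in the SH+ arm, so the intervention criterion removes people mainly from that arm, and removes them by their own behaviour after randomisation. The remaining SH+ attenders are set against nearly all assessed controls, including those who would not have attended had they been offered the course.

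If attenders and non-attenders differ in their underlying risk of a psychiatric diagnosis, PP and ITT will differ even when SH+ does nothing. A PP result that agrees with ITT is then weak evidence of robustness, and one that disagrees cannot be interpreted. At stake is the reading of the supportive analysis. The primary test is not affected.

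**Working it through.** **Inputs from the protocol** (Sample size and power calculations): risk of 25% at six months, a design difference of 10 points (25% v 15%), 250 evaluable per arm, 80% power, significance level 0.05, and 300 randomised per arm.

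**Inputs assumed**, because the protocol gives neither: the share *f* of SH+ participants who do not attend, and the ratio *R* of non-attenders' risk to attenders' risk.

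**1. The protocol's own figure.** Two-sided, pooled variance, no continuity correction:

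n per arm = [1.96·√(2·0.20·0.80) + 0.8416·√(0.25·0.75 + 0.15·0.85)]² / 0.10² = (1.1087 + 0.4724)² / 0.01 ≈ 250.

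This reproduces 250 per arm and 80% power. The step to 600 implies a loss of 1 − 500/600 = 16.7%.

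**2. PP with no true effect.** Both arms have a risk of 25%, so the attenders' risk *a* satisfies (1 − f)·a + f·R·a = 0.25, which gives

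a = 0.25 / (1 − f + f·R).

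PP compares *a* in 250·(1 − f) attenders with 25% in 250 controls.

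**3. One case in full: f = 40%, R = 2.**
- a = 0.25/1.4 = 17.9%, so the apparent difference is 7.1 points (RR 0.71), with 150 v 250 people.
- Pooled risk = (150·0.1786 + 250·0.25)/400 = 0.2232.
- SE for the test = √[0.2232·0.7768·(1/150 + 1/250)] = 0.0430.
- SE of the difference = √[0.1786·0.8214/150 + 0.25·0.75/250] = 0.0416.
- Chance of a significant result favouring SH+ = Φ[(0.0714 − 1.96·0.0430)/0.0416] = Φ(−0.31) ≈ 38%.

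**4. Range, same formulas.**

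| Non-attendance f | Risk ratio R | SH+ attenders' risk | Spurious benefit (points) | Chance of significance favouring SH+ |
|---|---|---|---|---|
| any | 1 | 25.0% | 0 | 2.5% |
| 10% | 2 | 22.7% | 2.3 | 8% |
| 20% | 1.5 | 22.7% | 2.3 | 8% |
| 20% | 2 | 20.8% | 4.2 | 18% |
| 30% | 1.5 | 21.7% | 3.3 | 12% |
| 30% | 2 | 19.2% | 5.8 | 28% |
| 40% | 1.5 | 20.8% | 4.2 | 15% |
| 40% | 2 | 17.9% | 7.1 | 38% |
| 30% | 0.67 | 27.7% | −2.7 | 0.5% (9% against SH+) |

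Simulation with 200,000 runs agrees for the cases checked: 17.8% (20%, R = 2), 11.7% (30%, R = 1.5), 28.6% (30%, R = 2) and 38.4% (40%, R = 2).

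**5. The 5% trigger.** It is counted over both arms: 0.05·600 = 30 people, or 30/300 = 10% of SH+ if all are in that arm. At f = 10% and R = 1.5, a = 0.25/1.05 = 23.8%, a shift of 1.2 points.

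**6. A complier-average causal effect under the same null.** It is the ITT difference divided by the difference between arms in the proportion receiving SH+. If no control receives SH+, this is 0/(1 − f) = 0 for every *f* and *R*, because no one is dropped from the randomised comparison.

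**The case against.** The strongest reply is that PP decides nothing. ITT is the stated basis, PP is additional, and the word *only* after *confirmatory purposes* limits it to corroboration. This stands. A reader might infer that a significant PP result could establish an effect that ITT does not show. The protocol gives it no such role.

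Three other strong readings also fail.
- **That PP excludes people from SH+ alone.** The rule names no arm. Its eligibility and assessment criteria remove people from both arms, and ETAU has some content of its own. The imbalance concerns the intervention criterion and is inferred from how the two arms are described.
- **That the bias usually favours SH+.** The document supports no direction. Under Potential risks it notes that participation may compete with housing, language and other demands, which leaves open whether non-attenders are at higher or lower risk.
- **That pooling the 5% trigger over arms is itself harmful.** If PP is prone to bias, skipping it when deviation is low avoids that bias, and the shift at the limit is small (1.2 points in the case above).

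The secondary Poisson model could adjust for measured prognostic factors, but it is described for the primary outcome in general and cannot remove unmeasured differences between attenders and non-attenders.

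The complier-average analysis is also open to criticism. With non-receipt almost confined to SH+, it is close to the ITT difference rescaled by attendance, so it adds little as a significance test. It also assumes that allocation has no effect in non-attenders. The SH+ section describes the self-help book as usable without the course, so that assumption could fail. Both points stand. Its value is as an estimate of the effect of receiving SH+ that keeps the randomised comparison.

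The attendance level that counts as fulfilling the protocol may be set in the SAP, so its absence here is no criticism.

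**Conclusion.** The concern holds in a limited form. The PP analysis is offered as a robustness check, but it mixes any treatment effect with selection of SH+ attenders, so neither agreement nor disagreement with ITT can be read as intended.

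Across 20–40% non-attendance and risk ratios of 1.5–2, the spurious benefit is about 2.3–7.1 points against a design effect of 10. The chance of a significant result favouring SH+ is 8–38% instead of 2.5%. With equal risk there is no bias. At a ratio of 0.67 and 30% non-attendance it is about 2.7 points against SH+.

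These sizes rest on assumed attendance and risk ratios, on the protocol's 25% risk, and on 250 assessed per arm with loss unrelated to outcome. ITT remains primary, so the trial's main conclusion is not at risk. *Confirmatory* is the wrong word for an analysis with this property.

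**What to change.** 1. State in General approach that the conclusion on the primary outcome rests on the ITT analysis.
2. Replace *confirmatory* with *supportive* or *descriptive* for PP, and show the numbers excluded by arm and by ground.
3. Add a complier-average causal effect for the primary outcome, with randomised arm as the instrument and recorded session attendance as receipt. Run it whatever the level of deviation.

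**Cost.** The changes are to wording, plus one added analysis. Session attendance must be recorded, which the protocol does not mention, and receipt must be defined before the data are unmasked.

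**Downside.** The estimate assumes that allocation has no effect in non-attenders, which could fail if they use the self-help book. Report it with that caveat, or add a sensitivity analysis that counts receiving the book as receipt.
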